CONFIDENTIAL: PROPRIETARY INFORMATION

Therapeutic monoclonal antibody combinations

In regions in which these are available, they will either be administered at the investigative site or patients will be informed as to where they can receive the antibodies. Use of the antibodies will be discussed with each patient in regions in which they are available. It is the patient's decision whether or not to receive the antibody combination.

Other Tests and Procedures

Patients will complete a smartphone-based diary at baseline and daily from day 2 (the second treatment day) through day 28 and days 1, 3 and 5 each subsequent week during the study. This will collect symptom information, adverse events, and study and concomitant medication administration. A patient who is unable to enter the diary data independently at baseline should not be enrolled in this study. If, however, the patient becomes physically unable to complete the diary during the course of the study, he or she may dictate responses to a caregiver or other companion; that the caregiver is completing the diary should be noted. If the patient is unable to respond to the questions during the course of the study, that should be so noted. A caregiver or companion should *not* complete the diary using assumed responses. The patient will be deemed not to have recovered on any day when he or she is unable to provide responses to the diary questions. If difficulties in use of the smartphone-based diary system occur, paper forms may be substituted for individual patients or in regions in which the smartphone-based system does not function properly.

If the baseline diary is completed on treatment day 1, rather than prior to treatment day 1, the patient should not complete the diary again that evening. The information to be collected is shown in Appendix 2.

At the baseline visit, patients will receive a kit which contains devices for remote patient monitoring. The kit includes:

- Electronic thermometer
- Pulse oximeter
- 6-lead ECG

The ECG device may be kept by the site personnel or by the patient, depending on convenience and logistics at each site.

All devices are FDA-cleared (i.e., approved via 510K pathway).

Patients and caregivers will be trained on use of all devices at their baseline visit and will be given additional documentation at the time of the baseline visit.

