In addition to analysis within the entire study population, subgroup analyses for secondary endpoints 1, 3-6 will be performed in the high risk population. Analysis for secondary endpoint 1 will focus primarily on the high risk and very high risk subgroups.

Where procedures and analyses described in the SAP differ from those in the protocol, those in the SAP take precedence.

This document focuses on analysis of part A of the study. Based on results of part A, study parameters including analysis parameters may be modified for part B. Changes from the current protocol and SAP will be formalized in amendments to the protocol and SAP, respectively.

Study: RHB-107-01 Page 4 of 28

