Calculation of time to sustained recovery requires completion of the symptom diary and determination that patient is afebrile. Before recovery is first documented, patients with missing symptom data will be considered as not recovered (i.e., last observation carried forward). If the diary is not completed on a given day after first meeting the definition of recovery as above, the recovery will still be considered sustained if symptom data is missing only intermittently. We will consider missing as intermittent if symptom data is missing for at most 4 consecutive days during the 28-day period when symptoms are expected to be recorded daily or 3 consecutive reporting days in the weeks after Day 28 when symptoms are recorded thrice a week until the end of study. If data gaps are longer than defined above, recovery will be considered as not sustained during these periods, and sustained recovery may be fully documented at a later time. If a patient is hospitalized, he or she will be considered as not recovered on those days, regardless of the reason for hospitalization. However, once a patient has completed the observation period defining sustained recovery (either 14 or 28 days), subsequent diary data gaps will not be considered as loss of sustained recovery status.

The comparison of the time to sustained recovery between active and placebo groups will be performed using log-rank test, at 5% significance level. The stratification factors used for randomization may be used if sample size per stratum is adequate. Kaplan-Meier plots of time to sustained recovery will be provided along with median estimates and hazard ratio (HR) will be estimated along with 95% confidence interval using stratified Cox regression model. Estimates of cumulative incidence of sustained recovery at certain time points (for example days 15, 29, 43 or 57) for each group, along with 95% confidence interval will be tabulated.

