## 18. Change from Analysis Specified in the Corresponding Protocol Version

The use of antipyretics will not be included in the assessment of the primary endpoint of sustained recovery as stated in the protocol. This is noted in the endpoint definition above and additional details of this change are provided in the appendix..

Study: RHB-107-01 Page 25 of 28

Part A Statistical Analysis Plan (Version 2.0)

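### After first recovery, SAP 12 counts short diary gaps outside hospital as continued recovery whatever the reason; protocol 5.2 counts days of inability to answer as not recovered, and the departure is undeclared

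*SAP*

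**What the plan says.** Protocol 5.2 lets a patient who becomes physically unable to fill in the diary dictate answers to a caregiver, who may not enter assumed responses. For a patient who cannot respond at all it says: "If the patient is unable to respond to the questions during the course of the study, that should be so noted". It then fixes the outcome: "The patient will be deemed not to have recovered on any day when he or she is unable to provide responses to the diary questions". It sets no minimum length of gap and makes no distinction between days before and after first recovery.

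SAP 12 handles missing diaries in stages.

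- Until recovery is met: "Before recovery is first documented, patients with missing symptom data will be considered as not recovered".
- After recovery is first met: "the recovery will still be considered sustained if symptom data is missing only intermittently". A gap is intermittent if "symptom data is missing for at most 4 consecutive days during the 28-day period", or for "3 consecutive reporting days in the weeks after Day 28". Longer gaps break the recovery.
- Days in hospital count as not recovered.
- Once the confirmation period (14 or 28 days) is complete, later gaps have no effect.

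The second rule does not ask why the diary is missing.

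On precedence, the SAP's study summary states: "Where procedures and analyses described in the SAP differ from those in the protocol, those in the SAP take precedence". Section 18, which lists changes from the protocol analysis, has one entry: "The use of antipyretics will not be included in the assessment of the primary endpoint of sustained recovery as stated in the protocol". The version 2.0 appendix does not mention the diary-gap rule.

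**The concern.** Inability to answer is not left as missing data in the protocol. It is given an outcome, not recovered. Read literally, SAP 12 gives the same day the opposite outcome whenever the gap is short, the patient is at home and recovery was met earlier. A program written from SAP 12 would keep the earlier recovery date.

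Two things are at stake. The first is the recovery date of each affected patient, in the endpoint that becomes primary in part B. The second is a decision that part A must inform, namely whether sustained recovery is confirmed over 14 or 28 days. A lapse between the end of the shorter window and the end of the longer one is what separates the two definitions, and the gap rule can hide it.

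**Working it through.** The plan gives no figure for how often such gaps occur, so the check compares the rules and works through examples. The gap limits come from SAP 12. The diary schedule (daily on days 2 to 28, then days 1, 3 and 5 of each week) comes from protocol 5.2.

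**1. The rules side by side, for a patient unable to answer**

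| Situation | Protocol 5.2 and 7.4.1 | SAP 12 |
|---|---|---|
| Before first recovery | not recovered | not recovered |
| In hospital | not recovered | not recovered |
| At home, recovery met, confirmation period running, gap within the limit | not recovered | recovered |
| As above, gap over the limit | not recovered | not recovered |
| Confirmation period complete | no effect on sustained recovery | no effect |

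The documents part in the third row only.

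**2. Effect on one recovery date (illustrative patient)**

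Recovery is first met on day 10. The patient is at home, noted as unable to respond on days 15 to 18, and meets the recovery criteria on every diary from day 19.

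- SAP: the gap is 18 − 15 + 1 = 4 days, within the limit, so the recovery day is 10.
- Protocol: days 15 to 18 are not recovered. They fall inside both the 14-day window (days 10 to 23) and the 28-day window (days 10 to 37), so the period restarts and the recovery day is 19.
- Difference: 19 − 10 = 9 days under either definition.

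**3. Effect on the 14- versus 28-day comparison (illustrative patient)**

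Recovery is first met on day 8. The patient is at home, unable to respond on days 24 to 27, and otherwise recovered.

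- Protocol, 14 days: the window is days 8 to 21 and the gap lies outside it, so the recovery day is 8.
- Protocol, 28 days: the window is days 8 to 35 and the gap lies inside it, so the recovery day is 28.
- SAP, either definition: the gap is 4 days, so the recovery day is 8.

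Under the protocol rule the two definitions differ by 28 − 8 = 20 days for this patient. Under the SAP they agree.

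**4. Calendar length of the limit after day 28**

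Reporting days are 29, 31, 33, 36, 38, 40, 43 and so on. Unanswered days = next answer − last answer − 1.

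- Missing 29, 31, 33: 36 − 28 − 1 = 7.
- Missing 31, 33, 36: 38 − 29 − 1 = 8.
- Missing 36, 38, 40: 43 − 33 − 1 = 9.

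The span is therefore 7 to 9 calendar days. Only three of them are scheduled diary days; the rest come from the protocol's own thrice-weekly schedule.

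**5. Weight of one patient**

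Part A plans 20 patients per arm, so one such patient is 1/20 = 5% of an arm.

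**The case against.** The case against acting has several parts.

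- **Few patients qualify.** The patient must have met recovery, be out of hospital, be unable even to dictate, resume answering within the limit, and then report no disqualifying symptom. Most diary symptom items ask for the worst severity over the previous 24 hours, so a patient who could not answer yesterday must already be well by today's diary. This stands, and it limits the point to a small group.
- **The SAP may be silent rather than contrary.** It speaks of uncompleted diaries and missing symptom data, not of noted inability. Its precedence clause applies only where the documents differ, and protocol 7.4.1 leaves missing-data handling to the SAP. SAP 4.1 and 5.3 also allow further rules at blinded review. This stands in part: the authors may have meant skipped diaries only. But the rule is worded without regard to reason and its only stated exception is hospital. Delegating missing-data handling also does not explain overriding an outcome that the protocol assigns.
- **Part A efficacy is descriptive.** Part B will have its own SAP, and the version 2.0 appendix offers sensitivity analyses with other recovery definitions. This stands. No confirmatory result rests on the rule yet.

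A reader might infer more than the documents support:

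- That the SAP treats every missing diary as recovery. It does not: missing days before first recovery, and gaps over the limit during confirmation, count as not recovered.
- That protocol 5.2 sets a rule for diaries simply skipped, which the SAP overturns. Section 5.2 contrasts patients who can dictate with patients who cannot respond; it gives no recovery rule for skipped diaries.
- That the SAP rule pulls the arms together. That would need relapse, and inability because of it, to differ between arms, and the documents give no such figures.

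**Conclusion.** The departure is real and undeclared, but narrow. It concerns patients at home, after first recovery and before confirmation, who cannot answer even by dictation for a gap within the limit. For such a patient the recovery date can be many days earlier under the SAP than under the protocol: 9 days in one example and 20 in another. The difference between the 14- and 28-day definitions can also vanish. These sizes rest on assumed patients. The number affected is probably very small, and the size and direction of any difference between arms cannot be computed. The point is worth settling before the part B SAP is written, because the endpoint becomes confirmatory there.

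**What to change.** In SAP 12, limit the intermittent-gap rule to diaries missed for reasons other than inability, and add: *Days on which the patient is recorded as unable to respond are days not recovered, as are days in hospital; the sustained-recovery period restarts afterwards.* Carry the rule into the part B SAP and capture inability there in a structured field, since the diary printed in protocol Appendix 2 has no such item. If the sponsor prefers the current rule, list it in section 18 with a justification, as was done for antipyretics.

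The text change is small. The price is slightly later recovery dates for the few patients affected. In part A the rule is only as good as the notes of inability, whose format the protocol does not specify. If those notes prove incomplete, the part A report should say so, and a sensitivity analysis counting all gaps between first recovery and confirmation as not recovered would bound the effect.

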#### 12.1 Correction of measured temperature to core temperature

The initial 10 patients' temperatures were measured with a biosticker adherent to the patient's chest. This provided data on surface temperature. This is not corrected to core temperature. In order to correct the measured biosticker temperature to core temperature, the biosticker temperatures closest in time to the oral temperature measurements performed by study staff (i.e., at each study visit) will be compared. The mean [median] difference across all patients for whom there are measurements will be calculated and then applied to correct the temperatures measured orally. Oral temperature is 0.5° C lower than the core (rectal) temperature, so the ultimate correction will be the mean [median] difference between biosticker and oral temperature plus 0.5° C.

To correct from measured oral or forehead temperature to core temperature, add 0.5° C to the measured temperature.

Study: RHB-107-01 Page 20 of 28

## 13. Analysis of Secondary Efficacy Endpoints

Analysis population: Analysis will be performed using the mITT and PP populations.

Analysis will be performed not only of symptom resolution and occurrence of new symptoms in aggregate, but also by individual symptoms assessed by investigators as related to COVID-19. This includes both the symptoms in the questionnaire and additional, less common symptoms which are recorded on the AE reports but attributed to COVID-19.

Items 1, 2, and 4 below are first-tier secondary objectives, to be analyzed initially. Items 3, and 5 are second tier objectives, which may be reported subsequently. Comparison between active treatment and placebo of the following secondary efficacy endpoints will be performed:

- 1) Incidence of hospitalization or death: the primary assessment of this endpoint will be among patients in the high risk group. This has been defined preliminarily above. The group may be redefined and recruitment for part B restricted based on analysis at the end of part A.
  Specific COVID-19 symptoms resulting in hospitalization will be tabulated by SOC, PT and severity. Depending on the number of patients hospitalized, this may be shown either as a table or listing.
  - Specific main COVID-19 symptoms resulting in death will be listed per patient.
- 2) The proportion of patients who are PCR-negative at each time point assessed, days 8, 15, 29 and 57 from the start of treatment (landmark analysis);
- 3) Time to resolution of individual disease-related symptoms present at baseline; COVID-19 symptoms, derived from the symptom questionnaires and those events entered as related to COVID-19 on the AE tables will be summarized as well using MedDRA classification by SOC, PT and severity as new COVID-19 symptoms and those worsening on study by at least one grade
- 4) Development of new disease-related symptoms or pneumonia on study;
- 5) Changes in laboratory markers of disease severity, i.e., oxygen saturation, CRP, lymphocyte count and D-dimer levels, from baseline to time points at which these are measured on study.

The time frame for all endpoints unless otherwise stated is from Day 1 (day of first dose of study medication) through study Day 57. The time to event endpoints will be analyzed using the methods described for the primary endpoint above.

Binary (Yes/No) endpoints (i.e., development of pneumonia diagnosed clinically, hospitalization and mortality) will be summarized using counts and percentages for each group. A 95% confidence interval will be constructed for each proportion. For endpoints other than mortality, (e.g, development of new

Study: RHB-107-01 Page 21 of 28

disease-related symptom on study), analysis will treat death before the event of interest as the most unfavorable possible outcome for this endpoint. Additional rules for handling missing data will be determined during blind review of the data and documented prior to unblinding.

Changes from baseline in laboratory markers (continuous variables) will be summarized by descriptive statistics. For oxygen saturation, which is measured twice daily throughout the study period, patterns will be presented visually. The median value for each subject from the preceding week will be used (e.g., for the Day 8, the median SpO2 value for Days 2-8 will be used). The daily SpO2 will be the subject's median of the 14 values collected (morning and evening). The morning and evening SpO2 will be the median of the 7 values at that time of day. Descriptive tables will be done for Days 1, 15, 22, 29, 36, 43, 50, 57.

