Temperature ^f		Measure and record temperature three times daily until afebrile for 14 days, then once daily in the evening until afebrile for 28 days							
Pulse oximetry ^f	Х	Twice daily through day 15			Thrice weekly through day 29				
Weight	Х								Х
Questionnaire and diary	Х	Every evening days 2-28; days 1, 3, 5 weekly thereafter ^g							
ECG ^h	Х			Х	Х		Х		
Nasal mid-turbinate (NMT) swab for SAR-CoV-2 PCR ⁱ	Х			Х	Х		Х		Х
CBC, biochem profile ^j , D-dimer, INR, PTT				Х	Х		Х		Х
CRP, D-dimer, troponin, ferritin	Х			Х	Х		Х		Х
Serum IgG and IgM antibodies to SARS-CoV-2	Х							С	Х
Alpha-1-antitrypsin and G6PD testing								Ck	X ^k
Study medication		<							
Adverse events ^I			Х	Х	X	Х	Х	Х	Х
Concomitant medications	Х		Х	Х	Х	Х	Х	Х	Х

Abbreviations: BL: Baseline; EOS: end of study; EOT: end of treatment

^aEnd of treatment visit, regardless of actual study day. Should generally be day 15, the day AFTER last dose of study medication.

^bEnd of study visit: generally day 57±4 from start of treatment, regardless of duration of treatment. If patient discontinues study participation prior to then, end of study procedures should be carried out, if possible, at the time of discontinuation from study, even if earlier than day 53.

^cType of contact/location: F: in facility: emergency department, clinic, COVID-19 special facility; H: home visit; H/F: option for either home or facility visit; T: televisit, either phone or video. Note: additional televisits may be arranged as needed. If patient returns to medical facility for outpatient visit, if possible, relevant procedures and tests should be performed at that time.

At all clinic and home health visits, temperature, pulse, respiratory rate, blood pressure, pulse oximetry and ECG measurements will be performed. Home health staff will obtain all vital signs independently of patient measurements, to verify that data are being collected accurately.

^dWithin 3 days prior to planned start of treatment: initial procedures include signing informed consent, review of medical history, review of documentation of COVID-19 disease and source/exposure, if available, height (measured or per patient), pregnancy test for women of childbearing potential, as detailed in section 5.2. When feasible, BL and day 1 procedures, i.e., start of treatment, should be completed on the same day.

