Under this amendment, the study procedures have been modified taking into account experience with the first patients entered into the study, as well as reasons patients have declined to participate. To date, symptoms have resolved in one to under three weeks. Patients have been resistant to the heavy monitoring and questioning in the original protocol, resulting in reluctance to participate in the study, withdrawal of several patients and poor compliance with study procedures. In order to enhance acceptability, accrual and compliance with the protocol, the duration of intensive vital sign monitoring is being reduced. In addition, the definition of sustained recovery is modified to take into account the patient compliance issue and experience to date with those patients who have recovered. If a substantial proportion of patients withdraws prior to the end of study *because* they feel better and the burden of study procedures is excessive, their efficacy results will be censored and those patients will be declared nonresponders. Temperature will be followed through 28 days after resolution of fever, if the patient is febrile, but with lower frequency from day 15 onward after resolution of fever.

Hospitalization or death has been moved to become the first secondary endpoint. FDA views this endpoint as that for which potential emergency use authorization is justified.

2. Objectives

Primary

Part A of the study: determination of the safety and tolerability of two dose levels and selection of an upamostat dose for part B. Part B of the study:

Primary objective: in the entire patient population, comparison between upamostat and placebo in time to sustained recovery from symptomatic illness in all patients. A patient will be considered to have recovered once he or she meets the following criteria:

- 1) is afebrile (<38.0° C core temperature) for at least 48 hours without use of antipyretics;
- 2) all symptoms have resolved or returned to pre-illness levels (e.g., if patient had respiratory compromise prior to the onset of COVID-19), except for:
 - i. fatigue, anosmia, ageusia or dysgeusia, which may be persistent at a level similar to that during the acute illness, i.e., the same level per symptom questionnaire;
 - ii. chest pain, cough or dyspnea, which if persistent must be at least one grade lower than at the start of treatment and no worse than grade 1 (mild).

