4.6 Replacement of Patients

Patients who are randomized but not treated will be replaced. Replacement patients will be given new randomization assignments; they will not receive the assignment of the replaced patient.

Patients who receive any study medication but discontinue with or without subsequent collection of data will not be replaced.

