7.1 Sample Size Considerations

Part A

In the first part of this study, two different dose levels of upamostat will be tested; randomization will be 1:1:1 to the two upamostat dose levels and placebo.

The objective of this part is to evaluate the tolerability of two dosing levels of upamostat in order to select the dose level that will be evaluated in the confirmatory Part B of the study.

The sample size for part A, consisting of 20 subjects per each arm (placebo, upamostat 200 mg qd, upamostat 400 mg qd) was not chosen for statistical power consideration, as there are no formal statistical inferences planned. The size of this part is judged adequate for the tolerability assessment.

Part B

After accrual to the first part of the study is completed and a determination as to which active arm to continue into the next part of the study is made, accrual will continue at a 3:2 ratio, active:placebo. A minimum total of 250 patients will be accrued to part B, 150 to the active arm using the regimen selected in part A of the study and 100 to placebo.

The sample size currently shown for part B was determined based on the primary endpoint, time to sustained recovery from COVID-19 illness, as defined in the primary objective. It was calculated that in order to detect a hazard ratio for sustained recovery=1.5 comparing the active group to placebo group with 3:2 allocation ratio, a total of 201 recovery events are required, to provide 80% power using a log-rank test at a two-sided significance level of 0.05. Assuming 80% sustained recovery rate in the control arm by end of follow-up (assumed equal follow-up of 57 days for all enrolled patients), it was calculated that in order to achieve the required number of events, the minimum number of patients enrolled will be 250 in total. As this study is defined as an operationally seamless phase 2/3 study, subjects from the part A of the study will not be combined with those in part B for the efficacy analysis. Therefore the target enrollment for part B is the total number of required subjects, namely 250 subjects in total, 150 and 100 for the active and placebo groups, respectively.

The target number of events for this event-based part B portion is 201, taking into account a non-binding futility analysis that will be performed when 50% of the information (primary events) have been realized.

Sample size re-assessment

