4.1 Missing Data

In general, no imputation of missing data will be done unless specified in the definition of the endpoints

below. Rules for censoring for time to event endpoints will also be described in detail in the definitions

below. Additional rules for imputation of missing data may be determined during blind review of the data

and documented prior to unblinding.

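### No hospitalization or vital status to day 57 is arranged for patients who leave the study, and the first secondary endpoint has no stated rule for unknown status

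*SAP*

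**What the plan says.** **Follow-up.** Protocol 4.5 keeps patients who stop study drug under observation to day 57, but also lets a patient withdraw from the study for any reason. For the second group, footnote b to protocol Table 1 says: "If patient discontinues study participation prior to then, end of study procedures should be carried out, if possible, at the time of discontinuation", even before day 53. No section sets a later call, record check or vital-status check for them. Protocol 4.6 says: "Patients who receive any study medication but discontinue with or without subsequent collection of data will not be replaced". Protocol 1.3 reports that the monitoring burden was already "resulting in reluctance to participate in the study, withdrawal of several patients and poor compliance with study procedures".

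**Analysis.** SAP 13: "Binary (Yes/No) endpoints (i.e., development of pneumonia diagnosed clinically, hospitalization and mortality) will be summarized using counts and percentages for each group", with a 95% confidence interval for each proportion. Protocol 7.4.2 adds population-level risk differences and leaves details to the SAP. The population is mITT, repeated on per-protocol patients, with emphasis on the high-risk group.

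**Missing data.** SAP 4.1: "In general, no imputation of missing data will be done unless specified in the definition of the endpoints". The definition of this endpoint specifies nothing for unknown status. The one rule nearby, in SAP 13, treats a known death before another event as the worst outcome. SAP 4.1, 5.3 and 13 leave further rules to blinded data review, to be documented before unblinding.

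**The concern.** The endpoint asks whether an event occurred by a fixed day, so a percentage is well defined only if status on that day is known or a rule covers patients for whom it is not. Here neither is secured for patients who leave the study. With no imputation, such a patient either stays in the denominator as a non-event or is left out, and the SAP does not say which. The primary endpoint, by contrast, has an explicit rule: patients lost before recovery are carried as unrecovered to day 57 (protocol 7.4.1, SAP 12).

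The protocol ties this endpoint to possible emergency use authorization (synopsis and section 1.3) and tests secondary endpoints in sequence (7.4.3). Its part A incidence would inform the part B sample size if the study is repowered (protocol 7.1, SAP 5.4) and may inform the high-risk definition (protocol 4.8). Unrecorded events would lower that incidence, and unequal withdrawal could shift the comparison between arms.

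**Working it through.** **The plan's own figures.** The documents give no sample size, power or dropout rate for hospitalization or death. The part B size belongs to the primary endpoint: "hazard ratio for sustained recovery=1.5 comparing the active group to placebo group with 3:2 allocation ratio, a total of 201 recovery events are required". The Schoenfeld formula gives (1.960 + 0.842)² / [0.6 × 0.4 × (ln 1.5)²] = 199 events, close to 201. With "Assuming 80% sustained recovery rate in the control arm by end of follow-up", 201 / 0.80 = 251, close to 250. The size reproduces, shows no separate allowance for withdrawal, and does not bear on this point.

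**Inputs for the illustration**
- Incidence p = 15%: protocol 4.8, a target for the high-risk control group if the study is repowered. Its use as the true rate is an assumption.
- High-risk patients in part B: the low-risk group is initially capped at 30% (protocol 4.1), so 0.70 × 250 = 175, or 105 active and 70 placebo at 3:2.
- Withdrawal w and the share s of a leaver's risk falling after exit: not in the documents, so assumed.

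**No true effect; w = 15% active, 5% placebo; s = 0.5; leaving unrelated to risk.** Per 100 patients:
- Active: observed events = 85 × 0.15 + 15 × 0.15 × 0.5 = 13.875
- Placebo: observed events = 95 × 0.15 + 5 × 0.15 × 0.5 = 14.625

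| Rule for leavers | Active | Placebo | Difference (points) |
|---|---|---|---|
| Counted event-free | 13.875 / 100 = 13.9% | 14.625 / 100 = 14.6% | −0.75 |
| All leavers excluded | 12.75 / 85 = 15.0% | 14.25 / 95 = 15.0% | 0 |
| Only leavers of unknown status excluded | 13.875 / 86.125 = 16.1% | 14.625 / 95.375 = 15.3% | +0.8 |

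The general form of the first row is (w_active − w_placebo) × s × p. With 20% versus 5% and all risk after exit it is 0.15 × 1 × 15 = 2.25 points in favour of active. In the third row, leavers with an event before exit are kept and event-free leavers are dropped, which raises the percentage. Kaplan-Meier, with leavers censored at exit, returns 15% in both arms under the same assumptions.

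**Equal withdrawal, true effect.** Assume 15% on placebo, 7.5% on active (assumed), 10% withdrawal per arm and all risk after exit:
- Event-free coding: 0.90 × (−7.5) = −6.8 points.
- Exclusion: completers' risk is p(1 − wm)/(1 − w), where m is the leavers' risk relative to their arm. The difference is −8.1 at m = 0.25, −7.5 at m = 1 and −6.7 at m = 2.
- Bounds, with leavers all events in one arm and none in the other: 6.75 − 23.5 = −16.8 to 16.75 − 13.5 = +3.3.

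**Part A, 20 per arm.** Take three events and two early leavers (assumed): 3/20 = 15.0% (exact 95% interval 3.2 to 37.9) or 3/18 = 16.7% (3.6 to 41.4). If both leavers had events, 5/20 = 25.0% (8.7 to 49.1).

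**The case against.** - **The rule is deferred.** The SAP commits to setting missing-data rules under blinding and documenting them before unblinding. That stands against any claim that the analysis is fixed without imputation. However, protocol 7.4.1 said the SAP would describe missing-data handling, and for this endpoint the SAP passes it on again. No analysis rule supplies status that was not collected.
- **The collection gap is read from silence.** Footnote b does not forbid later contact, and protocol 4.6 contemplates data after discontinuation. Protocol section 6 assesses adverse events through day 57, COVID-19 hospitalizations and deaths are followed like serious adverse events (protocol 7.5, SAP 15), and SAP 16.2 uses hospital records. The consent pages are not among the documents reviewed and may provide for contact after withdrawal. All this is fair, but none of these sections sets a contact for a patient who has left, and records are obtained only for patients already known to be hospitalized.
- **Protocol 1.3 has a rule for some leavers.** If many leave because they feel better, their efficacy results are censored and they become nonresponders. That sentence concerns sustained recovery and has no defined meaning for hospitalization.
- **The effect is small.** For 105 versus 70 patients at 15%, the standard error is √[0.15 × 0.85 × (1/105 + 1/70)] = 5.5 points, so 0.75 points is about 0.14 of it and 2.25 about 0.41. Equal withdrawal under event-free coding shrinks the difference, which is conservative. This stands.
- **Scope.** This SAP covers a descriptive part A (SAP 1 and 4.3), and a part B SAP is to follow. This stands, and puts the main consequence in part B.

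**Conclusion.** The point holds in this form: the plan arranges no hospitalization or vital status to day 57 after a patient leaves the study, and it leaves the denominator and the rule for unknown status open until blinded review. A reader might infer that the SAP scores early leavers as event-free, or that collection after exit is ruled out. The documents support neither: no coding is stated, and the missing follow-up is an absence of provision, confined to patients who leave the study rather than those who only stop drug.

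The effect is minor for part A and more relevant to part B and to repowering. Its size and sign depend on the rule: −0.75, 0 or +0.8 points in the same illustration. That rests on assumed withdrawal of 15% versus 5%, half the risk after exit, and the 15% target taken as the true rate. The documents report several withdrawals but no rate. The change is worth making before part B enrols, because uncollected status may not be recoverable afterwards.

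**What to change.** 1. In protocol 4.5 and footnote b to Table 1, separate stopping study procedures from withdrawing consent to all contact. For patients who stop procedures but agree, obtain hospitalization and vital status at day 57 by one telephone contact or record check. Amend the consent wording if it does not already allow this.
2. In SAP 13 and the part B SAP, state that the denominator is every mITT patient in the risk group analysed. Estimate the day-57 risk per arm and its difference by Kaplan-Meier, censoring unknown status at last contact. Death is part of the endpoint, so it raises no competing-risk problem.
3. Add a sensitivity analysis counting unknown status as an event, or a best-case and worst-case pair, because Kaplan-Meier assumes that leaving is unrelated to later risk. That is doubtful if patients leave because they feel better.

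The cost is wording in the protocol, the SAP and possibly the consent form, a few extra contacts, an interval slightly wider than for the crude percentage, and reliance on the censoring assumption.
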